We approached the assessment of the “Stop Use” and “Do Not Use” warnings differently. In the DFL, the “Stop Use” warnings are related to pregnancy, acute rhabdomyolysis, myopathy and hepatitis, conditions for which stopping the drug immediately are critical. In contrast, the “Do Not Use” warnings have a much lower risk for harm if treatment is continued for a period following the event. Prescription Crestor 5 mg is actually indicated for a number of the “Do Not Use” criteria. While we want to see participants with a “Do Not Use” warning stop drug immediately, should they continue for a period of time prior to completing a TASS reorder assessment, the likelihood of harm remains low.

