 - (a) Note that a "Do Not Use" outcome occurs whenever a participant meets DFL or LDL-C lowering criteria that would require the participant to stop treatment. This means that a participant who meets a *Stop Use* or *Do Not Use* criterion from the DFL will receive the same "Do Not Use" outcome and be evaluated as "Do Not Use" for the purpose of the second co-primary endpoint. For the purpose of evaluation of the secondary endpoints, the reasons for the "Do Not Use" outcomes will be assessed in order to place them in the appropriate category for evaluation. In other words, participants who received a "Do Not Use" outcome due to a *Stop Use* criterion in the DFL will be assigned to the *Stop Use* category for evaluation.
- 3 For participants who get an "Ask a Doctor" outcome during the use period, they will be given until the end of the 6-month use period to speak to a doctor. Since participants

cannot reorder drug until they speak to the doctor, the risk of continuing them in the study is low. Importantly, allowing them to continue for the full 6 months gives us the opportunity to assess whether they will contact a doctor at some point.

- (a) If a doctor gives them permission to continue therapy, they will take the reorder assessment and indicate that they had permission to continue therapy. They will be able to reorder medication and continue in the study. Their final use assessment will be performed at the end of the 6-month use period during their Virtual Visit 2.
- (b) If they do not take another reorder assessment, they will be seen at the end of the 6-month use period and their “Ask a Doctor” assessment will be used as their TASS final use assessment.

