4.1.3.1 Missing Dates

In some instances, a participant’s medical portal may only reflect the month and year a diagnostic test was conducted. While this information is sufficient to assess whether a diagnostic test was conducted within the required time frame according to the study, any dates with a missing day for a diagnostic test will be imputed using the following:

Missing Date	Imputation
Missing day (ex. March 2020)	The missing day will be imputed as the first day of the month.

For the exploratory efficacy analyses where time (in days) to compliance with a “Stop Use”, “Do Not Use” or “Ask a Doctor” warning is assessed, handling of missing dates will be done in accordance with the scenarios shown in [Appendix F](#).

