As discussed in [Section 3.2.6](#), the data for assessing the Stop Use timeframe will come from the Targeted Medical and Medication History Form at Visit 2. For those participants who correctly self-identify as having a “Stop Use” warning and stop the medication, the date from when a participant identifies a “Stop Use” warning to the date the medication was stopped will be calculated, in number of days, as follows:

$$\text{Time from having a “Stop Use” warning to stopping the medication (in days)} = (\text{Date medication was stopped} - \text{Date of “Stop Use” warning}) + 1 \text{ Day}$$

Descriptive statistics for time (in days) from having a “Stop Use” warning to stopping the medication will be summarized on the PP population overall and by subgroups.

For those participants who correctly self-identify as having a “Stop Use” warning and contact a doctor, the date from when a participant identifies a “Stop Use” warning to the date their doctor was contacted will be calculated, in number of days, as follows:

$$\text{Time from having a “Stop Use” warning to contacting a doctor (in days)} = (\text{Date doctor contacted} - \text{Date of “Stop Use” warning}) + 1 \text{ Day}$$

Descriptive statistics for time (in days) from having a “Stop Use” warning to contacting a doctor will be summarized on the PP population overall and by subgroups.

Timeframe for Complying with Do Not Use Warning

As discussed in [Section 3.2.7](#), the data for assessing the “Do Not Use” timeframe will come from the Targeted Medical and Medication History Form at Visit 2. For those participants who correctly self-identify as having a “Do Not Use” warning and stop the medication, the date from when a participant identifies a “Do Not Use” warning to the date the medication was stopped will be calculated, in number of days, as follows:

$$\text{Time from having a “Do Not Use” warning to stopping the medication (in days)} = \frac{\text{(Date medication was stopped – Date of “Do Not Use” warning)}}{+ 1 \text{ Day}}$$

Descriptive statistics for time (in days) from having a “Do Not Use” warning and stopping the medication will be summarized on the PP population overall and by subgroups.

Compliance with Speak to a Doctor Component of Ask a Doctor Before Use Warning

The percentage of participants who correctly self-identify as having an “Ask a Doctor Before Use” warning and speak to a doctor will be calculated as follows:

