 - a. If the ASCVD risk score is within the designated range, then the CMOG total cholesterol, HDL-C and SBP values are acceptable.
 - b. If the ASCVD risk score is outside the designated range, then the CMOG total cholesterol, HDL-C and SBP are not acceptable.
3. Assess whether the difference in initial TASS outcomes is due solely to the CMOG laboratory or blood pressure data not generating a REF. If this is true, apply variability criteria to the CMOG laboratory or BP value to determine if the REF is generated.
 - a. If REF generated, then the CMOG values are acceptable.
 - b. If REF not generated, then the CMOG values are not acceptable.

14 APPENDIX F – IMPUTATION OF MISSING KEY DATES FROM THE TARGETED MEDICAL AND MEDICATION HISTORY FORM.

Scenarios	Day of Event [1]	Date Stopped Medication [2]	Date Spoke to the Doctor [2]	Imputation
Missing Date for Day Action Taken (Stopped Medication or Spoke to Doctor)	Yes	Only Month and Year	Yes	Date Stopped Medication imputed as the date halfway between date of the event and the end of the month
	Yes	Only Month and Year	Only Year	Date Stopped Medication imputed as the date halfway between date of the event and the end of the month. No imputation for Date Spoke to Doctor
	Yes	Only Year	Yes	No imputation for Date Stopped Medication
	Yes	Yes	Only Month and Year	Date Spoke to Doctor imputed as the date halfway between date of the event and the end of the month
	Yes	Yes	Only Year	No imputation for Date Spoke to Doctor
	Yes	Only Month and Year	Only Month and Year	Date Stopped Medication imputed as the date halfway between date of the event and the end of the month. Date Spoke to Doctor imputed as the date halfway between date of the event and the end of the month
	Yes	Only Year	Only Month and Year	No imputation for Date Stopped Medication Date Spoke to Doctor imputed as the date halfway between date of the event and the end of the month
	Yes	Only Year	Only Year	No imputation for Date Stopped Medication No imputation for Date Spoke to Doctor
Missing Date of the Event	Only Month and Year	Yes	Yes	Date of Event imputed as the date halfway between the beginning of the month and earliest date of action (i.e., earliest of the date medication stopped or spoke to doctor)
	Only Month and Year	Only Month and Year	Yes	Date of Event imputed as the date halfway between the beginning of the month and the date spoke to doctor. Date Stopped Medication imputed as the date halfway between date of

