Scenarios	Day of Event [1]	Date Stopped Medication [2]	Date Spoke to the Doctor [2]	Imputation
				the event and the end of the month.
	Only Month and Year	Yes	Only Month and Year	Date of Event imputed as the date halfway between the beginning of the month and the date medication stopped. Date Spoke to Doctor imputed as the date halfway between date of the event and the end of the month
	Only Month and Year	Only Month and Year	Only Month and Year	Date of Event imputed as beginning of the month. Date of each action imputed as end of the month.
	Only Year	Yes	Yes	No imputation for Date of Event
	Only Year	Yes	Only Month and Year	No imputation for Date of Event Date Spoke to Doctor imputed as the date halfway between date of the stopped medication and the end of the month
	Only Year	Only Month and Year	Yes	No imputation for Date of Event Date Stopped Medication imputed as the date halfway between date of spoke to doctor and the end of the month.

[1] Event dates will be obtained from the Targeted Medical and Medication History Form or from the AE form of the respective AE. AE dates will be start dates of the event.

[2] Action dates only imputed if the participant took the respective action.

15 APPENDIX G - SCENARIOS FOR LDL-C VALUES AND INCLUSION OF VALUES IN PROPOSED ANALYSES OF LDL-C

Scenario	Primary LDL-C Analysis	Sensitivity Analyses				
		#1	#2	#3	#4	
*An LDL-C retest will be performed at Visit 2 and used for this analysis.						
^ Missing LDL-C value will be imputed according to missing data imputation method.						
"OK to Use" Outcome Scenarios						
1. Completes 6-month trial with an “OK to Use” outcome (based on participant’s outcome) and has entered an LDL-C value into the Web App during a reorder assessment verified by source document for Visit 2	X	X	X	X	X	
2. Completes 6-month trial with an “OK to Use” outcome (based on participant’s outcome) and has entered an LDL-C value into the Web App during a reorder assessment NOT verified by source document for Visit 2	X*	X*	X*	X*	X	
3. Completes 6-month trial with an “OK to Use” outcome (based on participant’s outcome) with an inadequate LDL-C response value entered into the Web App during an early reorder assessment but at a subsequent reorder assessment enters an adequate LDL-C response value into the Web App verified by source document for Visit 2	X	X	X	X	X	

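### SAP Appendix F does not say which month its halfway rule uses or keep an imputed date in its recorded month, so some exploratory times to act come out impossibly short

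*SAP*

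**What the plan says.** SAP 4.1.3.1 (Missing Dates) limits the scope: "For the exploratory efficacy analyses where time (in days) to compliance with a" Stop Use, Do Not Use or Ask a Doctor warning, "handling of missing dates will be done in accordance with the scenarios shown in" Appendix F.

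For a known event date and an action date with month and year only, Appendix F gives two parallel rules:

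- Stopping: "Date Stopped Medication imputed as the date halfway between date of the event and the end of the month".
- Doctor contact: "Date Spoke to Doctor imputed as the date halfway between date of the event and the end of the month".

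If instead the event day is missing, the event is placed midway between the start of the month and the earliest known action. The only stated limit on imputing actions is note 2: "Action dates only imputed if the participant took the respective action".

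SAP 4.2.4 then takes the time from the warning "to the date the medication was stopped will be calculated, in number of days", adding one day. Contact with a doctor is timed in the same way.

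**The concern.** A date known to its month should be imputed inside that month. The midpoint between the event and a month-end satisfies this automatically only when both dates share a month. Once the action month is later, the midpoint can fall before the action month begins. The derived time is then shorter than any value compatible with what the participant reported.

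The plan foresees actions in a later month. Protocol 9.4.2.1 says of participants with an Ask a Doctor outcome that "they will be given until the end of the 6-month use period to speak to a doctor". Protocol 8.1 considers participants with a Do Not Use warning "should they continue for a period of time prior to completing a TASS reorder assessment", and supplies last 45 or 90 days. The timing data come from the history form completed at Visit 2, which can be months after the event.

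At stake is the description of how quickly consumers respond to label warnings, an exploratory objective in SAP 1.1. There is also a reproducibility problem: two programmers could both follow the text and derive different times for the same person.

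**Working it through.** The documents give no figure for this rule, so there is nothing to reproduce. The check applies the rule by calendar arithmetic.

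**Notation.** E is the event date; S and T are the first and last days of the recorded action month. Time = action date − E + 1 (SAP 4.2.4). Half-days are rounded down unless stated; Appendix F gives no rounding rule.

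- Reading A (*the month* is the action month): imputed date = E + (T − E)/2.
- Reading B (*the month* is the event month): the same formula, with the last day of the event month in place of T.
- Possible range for a later-month action: from S − E + 1 to T − E + 1.

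**Example: event 5 January, stopped in March, non-leap year.**

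- S − E = 55 and T − E = 85, so the possible range is 56 to 86 days.
- Reading A: 85/2 = 42.5, rounded to 42. The imputed date is 16 February and the time 43 days, 13 below the minimum.
- Reading B: 31 January − 5 January = 26, and half is 13. The imputed date is 18 January and the time 14 days, 42 below the minimum.

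**When reading A fails.** The midpoint precedes S when (S − E) > (T − S). In the example, 55 > 30. For an event on 1 March with action in April, 31 > 29, so the rule gives 31 March and 31 days against a minimum of 32.

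**All 365 event dates of 2022, by calendar-month gap.** The shortfall is the number of days below the minimum possible time, among failing dates.

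| Gap in months | Reading A: outside recorded month | Shortfall, A | Reading B: outside | Mean shortfall, B |
|---|---|---|---|---|
| 0 | 0 | none | 0 | none |
| 1 | 14 (3.8%) | 1 to 2 | 365 | 8.6 |
| 2 | 363 (99.5%) | 1 to 18, mean 8.7 | 365 | 39.0 |
| 3 | 365 | 15 to 33, mean 23.8 | 365 | 69.4 |

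With half-days rounded up, the reading A counts at one and two months become 7 and 358.

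**Mirror case: event known as March, earliest action a doctor contact on 20 May.** From 1 March to 20 May is 80 days, and half is 40. The event is imputed at 10 April, outside March. The time is 40 + 1 = 41 days. The minimum possible, from 31 March, is 50 + 1 = 51.

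**The case against.** Several points on the other side stand.

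- A reader might infer that the rule works only when event and action share a month. That is too strong. The action month is the more natural reading of a row about a date known to month and year, and under it adjacent months fail for 3.8% of event dates, by 1 to 2 days. The 14-day figure needs the event-month reading.
- A reader might infer that slow responders as a group are made to look fast. Only those with a partial date are touched. Complete dates are used as recorded, and action dates known only by year are not imputed.
- Appendix F does not shorten throughout. When all three dates have month and year only, the event goes to the start of the month and the actions to the end, which gives the longest interval.
- Long gaps are least likely for Stop Use. Timing is computed only for those who self-identify the warning and act (SAP 4.2.4). The day 60 and day 120 contacts look for these criteria, and a criterion first found by the clinician counts as a failure to self-identify (SAP 3.2.6). Long gaps remain plausible for Do Not Use stopping and for doctor contact.
- A reader might infer a material shift in the reported mean. The documents do not say how many partial dates to expect, so this cannot be sized. SAP 4.1.1 also plans the median and quartiles, which one or two values move less.

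These points limit scope and consequence. They do not repair the rule: nothing in either document confines it to same-month cases or bounds the result.

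**Conclusion.** The rule as written can produce dates that contradict the recorded month. Under the action-month reading, failure is rare at one month and almost universal from about two. Under the event-month reading it occurs for every later-month action. Where the known-event and event-day rows fail, the error always runs toward a shorter time to act, and it grows with the true delay.

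The consequence is small. The affected summaries are exploratory and descriptive, with no hypothesis or success threshold. The secondary warning-compliance endpoints in SAP 4.2.3 count participants and do not use these times, and no co-primary endpoint uses Appendix F. A claim that the trial's evidence on warning compliance is compromised would not be supported.

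The counts assume the 2022 calendar and an even spread over event dates. They describe how the rule behaves and do not predict how many participants it will affect.

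**What to change.** In Appendix F, define *the month* as the recorded month of the date being imputed, require every imputed date to lie in that month, and set the order of steps:

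1. **Event day missing.** Impute it first, as the midpoint between the first day of the event month and the earlier of (a) the earliest known action date and (b) the last day of the event month.
2. **Action day missing.** Then impute the midpoint between the later of (a) the event date and (b) the first day of the action month, and the last day of the action month.

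State how half-days are rounded. The row with all three dates month-only can stay as written. Rows with a year-only event yield no time and are not at issue.

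Check, rounding down:

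- Event 5 January, stopped in March: midpoint of 1 and 31 March is 16 March, so 55 + 15 + 1 = 71 days, within 56 to 86.
- Event in March, doctor contact 20 May: the event becomes 16 March, so 65 + 1 = 66 days, within 51 to 81.
- Event 10 March, action in March: 20 March, 11 days, as under the present rule. Same-month cases do not change.

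The cost is a short paragraph in Appendix F and a small change to the derivation code. It needs no new data and changes no co-primary or secondary analysis.
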